## 6.2 SELECTION OF DOSES FOR SUBJECT COHORTS

The starting dose for Cohort 1 of 20 pmol phospholipid/kg body weight was selected as described in Section 1.3. Dose administration for each cohort will occur such that there is an observational period of 3 days between dosing the first, second, and third subject. This observational period will allow for the monitoring of any dose-limiting toxicities (DLTs) (see Section 6.3) in at least 1 subject treated with UNEX-42. The Data Monitoring Committee

(DMC) will make dose escalation recommendations based on review of safety data between cohorts (see Section 10.7).

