Drug Dosage and Formulation	
UNEX-42 is a preparation of extracellular vesicles that are secreted from human bone marrow-derived mesenchymal stem cells suspended in phosphate-buffered saline. UNEX-42 is a clear liquid that is provided in appropriately sized vials and stored at -70±10°C prior to use.
 
UNEX-42 will be administered via IV infusion. Three dose cohorts will be evaluated:
 
 
Cohort 1: 1 administration of 20 pmol phospholipid/kg body weight
 
Cohort 2: 1 administration of 60 pmol phospholipid/kg body weight
 
Cohort 3: 1 administration of 200 pmol phospholipid/kg body weight
 

Control Group	Placebo (phosphate-buffered saline)
Route of Administration	IV infusion (via umbilical/central/peripheral IV line)

Procedures	
Subjects will be assessed during Screening and Baseline (prior to randomization) to determine eligibility for the study. After randomization, subjects will be monitored in the hospital through 40 Weeks PMA or the time of hospital discharge (whichever comes first).
 
The following efficacy and safety assessments will occur during the course of the study:
 
Efficacy Assessments: incidence and severity of BPD, duration of hospitalization, duration of mechanical ventilation, duration of supplemental oxygen therapy, duration of postnatal steroids, tracheal aspirate, and Respiratory Severity Score.
 
Safety Assessments: physical examination, vital signs, adverse events, predefined complications of prematurity, clinical laboratory parameters, and chest x-ray.
 
Enrollment between cohorts will pause for data review by a Data Monitoring Committee to evaluate the data available after each of the first 2 cohorts have been enrolled. Dose administration for Cohort 1 will occur such that there is an observational period of 3 days between dosing the first, second, and third subject to assure the opportunity for safety assessments in at least 1 subject on active treatment. This procedure will be followed for each cohort.
 
Subjects that complete the Post-treatment Phase (including those that are discharged from hospital prior to 40 Weeks PMA) will continue into the Long-term Outcome Phase and will be assessed through 1 year of corrected age.

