c Subjects that discontinue the study prematurely should have the 40 Weeks PMA/Hospital Discharge assessments performed if possible. Subjects that complete the 40 Weeks PMA assessment or are discharged from hospital will continue into the Long-term Outcome Phase shown in [Table 3-2](#).

d The most recent CXRs prior to randomization and 36 Weeks PMA can be used.

e Clinical laboratory assessments will consist of a complete blood count, differential count, sodium, potassium, chloride, bicarbonate, blood urea nitrogen, creatinine, aspartate aminotransferase, alanine aminotransferase, and total and indirect bilirubin. For Baseline, the clinical laboratory assessments may utilize the laboratory assessments obtained as standard of care treatment within the last 24 hours in lieu of drawing blood for the sole purpose of the study. Any study-required blood tests should be obtained at the same time a blood sample is being collected for clinical purposes, if possible.

f On Day 1, vital signs are to be collected just prior to dosing, at the midpoint of dosing, just after the end of dosing, and at least once every hour for the first 4 hours after dosing is completed. Vital signs are to include heart rate, respiratory rate (either spontaneous rate or the sum of spontaneous rate and mechanically delivered rate), and systemic blood pressure (systolic and diastolic).

g Mean airway pressure is only to be collected from subjects undergoing mechanical ventilation.

h Oxygen saturation should be measured from a post-ductal location and should be consistently obtained post-ductally throughout the study period.

i The RSS should be calculated as the mean airway pressure multiplied by FiO2. Mean airway pressure and FiO2 will be collected at the same time, and the RSS will only be calculated when the subject has an obtainable mean airway pressure.

j A tracheal aspirate will be collected as possible at Baseline (prior to dosing), 72 hours postdose (if still intubated), and 7 days postdose (if still intubated).

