### **3.3.2.6 Clinical Laboratory Parameters**

Blood samples for the clinical chemistry and hematology analyses will be collected at Baseline (randomization) and repeated at the 72 hours postdose and the 36 Weeks PMA assessments to evaluate for study treatment-emergent changes. For Baseline, the clinical laboratory assessments may utilize the laboratory assessments obtained as standard of care treatment within the last 24 hours in lieu of drawing blood for the sole purpose of the study. Any study-required blood tests should be obtained at the same time a blood sample is being collected for clinical purposes, if possible. Values for the following parameters will be obtained:

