### **6.3 DOSE-LIMITING TOXICITY**

DLTs will be used to inform dosing decisions; however, no DLTs have been observed during nonclinical development of UNEX-42. Therefore, for the purposes of this study, only an estimate of possible dose-limiting events can be made. As a result, DLTs will be defined as any of the following toxicities assessed by the Investigator and/or Sponsor as at least possibly related to UNEX-42 based on the time to onset following UNEX-42 administration and judged not to be related to the underlying condition or any concomitant medications by the Investigator and/or Sponsor:

- A treatment-emergent adverse event (TEAE) that is of potential clinical significance such that further dose escalation would expose subjects to unacceptable risk.
- Increased liver enzymes (Grade 2 or higher, using the National Cancer Institute (NCI) Common Terminology Criteria for Adverse Events (CTCAE) Version 5.0 as guidance) or any evidence of hepatic failure.
- Pulmonary toxicity, worsening respiratory distress, or other acute exacerbation of pulmonary function requiring ventilatory support or escalation of care.

In addition, the DMC may identify as a DLT, any TEAE occurring in subjects treated with UNEX-42 at any time during the study. Each DLT must be recorded in the eCRF as an AE. In addition, any DLT that meets criteria for a SAE must be reported to the Sponsor in an expedited manner as described in Section 9.4.

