## **9.4      REPORTING RESPONSIBILITIES OF THE INVESTIGATOR**

Sites should enter initial or follow-up SAE information regardless of causality or expectedness into the Sponsor's Electronic Data Capture (EDC) system (primary method) within 24 hours of awareness of an SAE. The SAE will be directly transmitted from the EDC system to the Argus

Safety Database. If the site is unable to enter the SAE electronically into EDC system, the alternative for reporting is submitting a scanned copy of the paper SAE Report Form via email to [REDACTED] within 24 hours of awareness. If the paper SAE Report Form is submitted, the site staff will also be required to enter the SAE data into the EDC system when the EDC becomes available. SAE source documents (eg, hospital discharge summary or death certificate) will be submitted by the site staff via email to [REDACTED]. The Investigator or Sponsor (if appropriate) must also notify their Institutional Review Board (IRB), Independent Ethics Committee (IEC), and/or other local equivalent body of the reported SAE, including any follow-up information. Copies of each report and documentation of IEC/IRB/local equivalent body notification and receipt will be kept in the Investigator's study file.

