## **9.5 SAFETY REPORTS**

In accordance with USA FDA regulations, the Sponsor or designee will notify the regulatory agency, Investigators, and/or IRBs and IECs of all relevant AEs (usually those that are considered to be possibly attributable to study drug and are both serious and unexpected) in accordance with the applicable regulations. The Investigator must report these AEs to their IRB/IEC in accordance with applicable regulations and guidelines set forth by the IRB/IEC.

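### Protocol 6.2 spaces the first three infants so that any DLT can be monitored, but nothing makes the next dose wait for the 72-hour liver result

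*Protocol*

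**What the plan says.** The Synopsis (Procedures) says that in each cohort "there is an observational period of 3 days between dosing the first, second, and third subject to assure the opportunity for safety assessments". The assessments meant are those of one or more infants given active drug. Protocol 6.2 repeats the gap and ties it to toxicity: "This observational period will allow for the monitoring of any dose-limiting toxicities (DLTs) (see Section 6.3) in at least 1 subject". The infant meant there is likewise one given UNEX-42.

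Protocol 6.3 says that DLTs inform dosing decisions. Its list includes "Increased liver enzymes (Grade 2 or higher" on CTCAE Version 5.0), if judged at least possibly related to UNEX-42 and not to the underlying condition or other drugs.

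According to Protocol 3.3.2.6, blood chemistry, which includes ALT and AST, is taken at Baseline and "repeated at the 72 hours postdose and the 36 Weeks PMA assessments". Table 3-1 places the 72-hour visit on Study Day 4 with a window of ±4 hours, and schedules no laboratory test at 24 hours or 7 days. Its footnote e adds: "Any study-required blood tests should be obtained at the same time a blood sample is being collected for clinical purposes, if possible".

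On reporting, 6.3 says "Each DLT must be recorded in the eCRF as an AE", and expedites only those DLTs that are also SAEs. Section 9.4 requires entry "within 24 hours of awareness of an SAE". Sponsor notices to investigators under 9.5 cover relevant AEs, "usually those that are considered to be possibly attributable to study drug and are both serious and unexpected". Section 15.1 has the investigator review laboratory results as they arrive. Under 10.4 and 10.7 the DMC reviews data between cohorts.

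**The concern.** The stagger is the one stated rule on when the next infant in a cohort may be dosed. Its declared purpose covers any DLT. One named DLT depends mainly on a laboratory value, and the scheduled sample for that value coincides with the end of the gap, or nearly so. A site that follows the timing rule exactly could therefore dose the next infant before the result exists, and on one reading before the blood is drawn.

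The study has about 6 centers (Protocol 3.4), so the next infant may be at a hospital that has no knowledge of the previous infant's results. The product had not been evaluated clinically before (Protocol 1.2), and the subjects are ventilated infants born before 27 weeks. At stake is one further infant per gap exposed to the same dose before a liver signal in the previous one has been seen.

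**Working it through.** **Inputs.** Gap: 3 days (6.2, Synopsis). Liver sample: 72 ± 4 hours (3.3.2.6, Table 3-1). Allocation: 2:1 in cohorts of 6 (3.5). Laboratory turnaround: not given; assumed 2 to 24 hours.

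**1. The plan's own counts.** 18 × 2/3 = 12 active, 18 × 1/3 = 6 placebo, and 6 × 2/3 = 4 active per cohort, as 3.5 states. The plan gives no figure for the timing of results against doses.

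**2. When the sample is drawn.** 72 − 4 = 68 hours to 72 + 4 = 76 hours after dosing. Footnote e asks sites to combine the draw with clinical sampling where possible, so either half of the window is ordinary practice.

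**3. Time from draw to the earliest next dose** = gap − draw time.

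| Reading of 3 days | Draw at 68 h | Draw at 76 h |
|---|---|---|
| 72 hours (next dose on Study Day 4) | 72 − 68 = +4 h | 72 − 76 = −4 h |
| About 96 hours (three full days between, next dose on Study Day 5) | 96 − 68 = +28 h | 96 − 76 = +20 h |

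On the first reading a draw in the later half of the window is on schedule but comes after the next dose is permitted.

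**4. When the result exists** = draw + turnaround. Earliest 68 + 2 = 70 hours; latest 76 + 24 = 100 hours. It can be up to 100 − 72 = 28 hours late on the first reading and up to 100 − 96 = 4 hours late on the second.

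**5. How many gaps matter.** There are two gaps per cohort, after subjects 1 and 2. The expected number that follow an active infant is 2 × 2/3 = 1.33.

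**6. Does any text supply the missing link?**
- 15.1: results are reviewed as they become available, with no tie to the next dose.
- 6.3: a DLT goes into the eCRF, so the sponsor can see it, but only a serious one has a deadline.
- 9.4 and 9.5: the 24-hour rule is for SAEs, and onward notices are usually for serious and unexpected events. A non-serious Grade 2 rise need not reach other sites before the next dose.
- 5.1: the IRT allocates study drug, but is not described as checking results.
- 5.3: drug-safety personnel are unblinded for safety reporting, with no stated role in releasing a dose.
- 10.4 and 10.7: the DMC acts between cohorts, after the staggered doses have been given.

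**The case against.** **The wording is soft.** To allow for monitoring, or to give an opportunity for assessment, does not promise a result in hand, and the criteria that are spelled out concern dose escalation. This stands. A reader might infer that the protocol contradicts itself; it does not. But DLTs are said to inform dosing decisions, and a gap that can close before a named DLT can be read serves its purpose only partly.

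**The 96-hour reading largely removes the timing clash.** This also stands: at a 24-hour turnaround the result is at most 4 hours late. The −4 hour figure also needs an eligible infant ready when the gap ends, and no accrual rate is given. Neither point supplies a rule that the dose must wait.

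**The link may sit elsewhere.** The DMC charter and the separate analysis plan for the DMC were not supplied, and 10.7 mentions an initial safety review period that the protocol does not define. Those documents could hold such a rule, although the protocol describes DMC review only between cohorts.

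**Liver toxicity need not wait for the 72-hour sample.** A reader might infer that the stagger is blind to it. That is too strong. The same DLT item includes evidence of hepatic failure, 9.3 allows extra tests, and other harms are covered by Day 1 vital signs and the 24-hour visit. Infusion stopping conditions and the power of the DMC or sponsor to stop the study (8.2) also remain.

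**The starting dose carries a 10-fold margin (1.3).** True for Cohort 1. At the top dose it no longer helps: 878 × 0.22 = 193 pmol/kg, against 200, though 878 was a volume limit, not a dose at which toxicity was seen.

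**A further reading to resist.** A reader might also infer that both gaps can pass with no active infant observed, since no hold follows subject 3. That requires a block of 6, where both placebos come first with probability 2/6 × 1/5 = 1/15 (6.7%) per cohort. With blocks of 3 it cannot occur. Section 5.2 gives no block size, so the documents do not support this as a finding.

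**Conclusion.** The point holds as a missing release rule. For a named DLT, the 3-day gap can end before the scheduled liver result is available, and nothing supplied requires anyone to wait for it or to report a non-serious DLT by a deadline. The draw is +4 to −4 hours from the next permitted dose if the gap is 72 hours, and 20 to 28 hours ahead of it if the gap is about 96 hours. The absence of a waiting rule does not depend on that reading or on block size; how late the result can be depends on the reading and on the assumed turnaround. The conclusion is limited to the supplied documents.

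The weight is moderate: at most two gaps per cohort, with other safeguards in place. Three subjects were randomized, all in Cohort 1, before the study was terminated (SAP 1.1). The gaps between subjects 1 to 3 are therefore the part of the plan that was used, but the documents do not say when those infants were dosed or what their results were. Nothing here implies that any infant was harmed. The value of the point is for the design and for any later protocol that reuses the stagger.

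**What to change.** Add to Protocol 6.2, with a matching sentence in the Synopsis:

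- State whether 3 days means 72 hours or three full days between doses.
- Before the next staggered infant is dosed at any site, the previous infant's 72-hour laboratory results must be available and reviewed, and any suspected DLT, serious or not, reported to the sponsor. Apply this whatever the arm, so that no one is unblinded.
- If a suspected DLT is reported, dosing holds at all sites until the Sponsor's Medical Monitor documents a decision, consulting the DMC if needed.
- If no 72-hour sample can be obtained, the Medical Monitor documents a decision on the other safety data.

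Separately, the sponsor should confirm that the restricted randomization specification places an active infant among the first two of each cohort.

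**Cost.** No new test is needed. With the assumed turnaround, the added delay per gap is max(0, draw + turnaround − gap): 0 to 28 hours beyond 72, or 0 to 4 beyond 96. Over two gaps that is 0 to 56 or 0 to 8 hours per cohort. A hold for a suspected DLT would add time that cannot be estimated. Eligibility spans postnatal days 3 to 14, which is 12 days counted inclusively, so 28 hours (28/24 = 1.2 days) is about 10% of it. An infant waiting near day 14 could be lost, as could one who is extubated, or expected to be, and so no longer meets 4.1.

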### **6.3 DOSE-LIMITING TOXICITY**

DLTs will be used to inform dosing decisions; however, no DLTs have been observed during nonclinical development of UNEX-42. Therefore, for the purposes of this study, only an estimate of possible dose-limiting events can be made. As a result, DLTs will be defined as any of the following toxicities assessed by the Investigator and/or Sponsor as at least possibly related to UNEX-42 based on the time to onset following UNEX-42 administration and judged not to be related to the underlying condition or any concomitant medications by the Investigator and/or Sponsor:

- A treatment-emergent adverse event (TEAE) that is of potential clinical significance such that further dose escalation would expose subjects to unacceptable risk.
- Increased liver enzymes (Grade 2 or higher, using the National Cancer Institute (NCI) Common Terminology Criteria for Adverse Events (CTCAE) Version 5.0 as guidance) or any evidence of hepatic failure.
- Pulmonary toxicity, worsening respiratory distress, or other acute exacerbation of pulmonary function requiring ventilatory support or escalation of care.

In addition, the DMC may identify as a DLT, any TEAE occurring in subjects treated with UNEX-42 at any time during the study. Each DLT must be recorded in the eCRF as an AE. In addition, any DLT that meets criteria for a SAE must be reported to the Sponsor in an expedited manner as described in Section 9.4.

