### 8.2 CRITERIA FOR TERMINATING THE STUDY

The study may be stopped at any time if, in the opinion of the DMC and/or Sponsor, continuation of the study represents a serious medical risk to the subjects. This may include, but is not limited to, the presence of serious, life-threatening, or fatal AEs or AEs that are unacceptable in nature, severity, or frequency. The Sponsor reserves the right to discontinue the study for any reason at any time.

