## **10.7 DATA MONITORING COMMITTEE**

A DMC will be established for the study, comprised of independent members including physicians knowledgeable in the treatment of complications of prematurity. A meeting will occur after each of the first 2 cohorts have been enrolled, as detailed in the DMC charter. The DMC will make dose escalation recommendations based on review of safety data. The criteria for dose escalation are based on the occurrence of AEs and/or DLTs that are unrelated to the underlying conditions or concomitant medications during the initial safety review period for each dosing cohort. The DMC may recommend stopping dose escalation at any point based on available data and sufficient scientific rationale.

All analyses will be prepared by an independent external consultant and reviewed by the DMC as defined in the DMC charter. The Sponsor (with the exception of Global Drug Safety and Regulatory Affairs personnel involved in safety reporting) will only have access to blinded study data until the completion of the study. A separate analysis plan will be prepared for these analyses.

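### The endpoints named for the DMC's escalation reviews leave out the seven predefined complications of prematurity, which become adverse events only if unusual or suspected

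*Protocol*

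**What the plan says.** **Status of the complications.** The Protocol Synopsis gives the safety assessments as "physical examination, vital signs, adverse events, predefined complications of prematurity, clinical laboratory parameters, and chest x-ray". Section 3.3.2.5 names seven complications and follows them from Baseline to 40 weeks PMA or discharge. Table 3-1 has them checked at Baseline and at every post-treatment visit.

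**Recording.** Under Protocol 9.1.1 a complication is entered as an AE or SAE only if it is unusual for that infant or there is a reasonable possibility that the drug caused it.

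**Review and escalation.** Section 6.2 says that the DMC "will make dose escalation recommendations based on review of safety data between cohorts". Section 10.4 pauses enrolment so that the DMC can look at the data then available, and identifies the endpoints for that review as those of 10.3.1. The complications are listed in 10.3.2. Section 10.7 leaves the details to a charter and a separate analysis plan, neither of which is in the documents. The SAP does not mention the DMC.

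**Context on attribution.** In 6.3 a listed toxicity is a DLT only if it is at least possibly related to UNEX-42 and also "judged not to be related to the underlying condition or any concomitant medications by the Investigator and/or Sponsor". One listed toxicity is "Pulmonary toxicity, worsening respiratory distress, or other acute exacerbation of pulmonary function requiring ventilatory support or escalation of care". Section 10.7 rests the escalation criteria on "AEs and/or DLTs that are unrelated to the underlying conditions or concomitant medications". Against this, 6.3 says that "the DMC may identify as a DLT, any TEAE occurring in subjects treated with UNEX-42 at any time during the study", and 10.7 says: "The DMC may recommend stopping dose escalation at any point based on available data".

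**The concern.** This is a first-in-human product given to ventilated infants born before 27 weeks. These complications are expected in such infants with or without the drug. If the drug made one of them more frequent, each case could still look ordinary, and an investigator blind to treatment would have little reason to suspect the drug. Section 9.1.1 then keeps the case out of the AE data. Judging cases one at a time cannot reveal an excess of ordinary events; setting the active infants beside the placebo infants can. The trial has concurrent placebo infants, but the endpoints named for the escalation review do not include the comparison for these events. What is at stake is the information in front of the DMC before a dose step of about three-fold.

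**Working it through.** The plan gives no figure for this point. The check is a count, a cross-reading and a look at what the missing table could show.

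**1. Count.**
- Section 3.3.2.5: sepsis, pneumothorax, PDA, necrotizing enterocolitis, intraventricular hemorrhage, periventricular leukomalacia, retinopathy of prematurity = 7.
- Section 10.3.1: TEAEs, all-cause mortality, treatment-related AEs, laboratory values, vital signs = 5.
- Complications named in 10.3.1: 0 of 7.

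**2. Routes to the DMC through the named endpoints.**

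| Event | Recorded as an AE (9.1.1)? | In the 10.3.1 set? |
|---|---|---|
| Respiratory worsening, even if blamed on the disease | Can be, as worsening of an existing condition | Yes, as a TEAE |
| Complication that is unusual or possibly drug-caused | Yes | Yes, as a TEAE |
| Complication that is fatal by 36 weeks PMA | Same rule as for any complication | The death, yes |
| Complication that is usual-looking, unsuspected and not fatal | No | No |

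Four of the five endpoints carry no attribution filter; only treatment-related AEs do. So for respiratory worsening recorded as a TEAE, the 6.3 rule affects the DLT label and not what the DMC sees. The last row is the gap.

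**3. DMC powers for the last row.** The power in 6.3 to name a DLT covers TEAEs only, so it does not reach an unrecorded complication. Two powers are not limited to TEAEs: stopping escalation on available data (10.7), and stopping the study where "in the opinion of the DMC and/or Sponsor, continuation of the study represents a serious medical risk to the subjects" (8.2). Both are discretionary and depend on the data being presented.

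**4. Dose steps.** 60/20 = 3.0 and 200/60 = 3.33.

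**5. What a by-arm table could show.** A cohort of 6 at 2:1 gives 6 × 2/3 = 4 active and 2 placebo, as in 3.5.
- Smallest two-sided Fisher p at 4 v 2 (4/4 v 0/2): 1/C(6,4) = 1/15 = 0.067.
- Smallest at 4 v 4 (cohort 2 against placebo from cohorts 1 and 2): 2/C(8,4) = 2/70 = 0.029. This assumes that the DMC tables pool placebo as 10.3 does for the summaries.
- Chance that the active rate exceeds the placebo rate at 4 v 2 with no drug effect, where A ~ Bin(4, p) and B ~ Bin(2, p): P(B=0)·P(A≥1) + P(B=1)·P(A≥3). At p = 0.5 this is 0.25 × 0.9375 + 0.5 × 0.3125 = 0.391.

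| Assumed shared rate p | 10% | 30% | 50% | 70% | 90% |
|---|---|---|---|---|---|
| P(active rate > placebo rate) | 0.279 | 0.408 | 0.391 | 0.363 | 0.181 |

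The rates are assumptions; the documents give none. A chance imbalance against the drug would appear in 18% to 41% of cohorts, so the table can inform judgement but is not a test.

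**The case against.** The strongest reply is that the DMC would see these events anyway. Section 10.4 and the Synopsis have it evaluate the data available, 6.2 and 10.7 speak of safety data, and the Synopsis counts the complications as safety assessments. Section 10.7 also requires members who know the treatment of complications of prematurity. The 10.4 pointer to 10.3.1 is not worded as exclusive, and a list of tables normally belongs in the charter or DMC analysis plan. All of this stands. It rules out the reading, which a reader might infer, that the DMC is barred from these data. It does not turn a likely inclusion into a stated one: where the protocol names endpoints for the review, these are missing.

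A second tempting inference is that 6.3 and 10.7 hide disease-like harm from the DMC or disable the escalation rule. The documents do not support it. DLTs only inform dosing decisions, no threshold is set, and recorded TEAEs and deaths come to the DMC whatever their attribution, summarised by dose cohort and placebo. The DMC may also relabel any TEAE in a treated infant or halt escalation. In 10.7 the words about unrelatedness could even attach to DLTs alone, although the natural reading covers AEs too. How strict the attribution bar should be in universally ventilated infants is a design preference.

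Third, a 4 v 2 table is very weak, and not every complication need have been diagnosed by an early review: follow-up can run to Day 116, and the protocol does not give the length of the initial safety review period. Both limits are real. They argue for labelling the table descriptive, not for leaving it out.

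**Conclusion.** The point holds in a narrow form and is a cheap improvement. A usual-looking, unsuspected, non-fatal complication of prematurity is neither a TEAE nor covered by any other endpoint that 10.4 names for the escalation review, although the protocol treats these complications as safety data. The size is the count: 0 of 7 complications among 5 named endpoints. With no event rates and no DLT threshold in the documents, an effect on escalation decisions cannot be calculated.

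The attribution wording in 6.3 and 10.7 is context. For events judged related to the underlying condition, the DMC must rely on its discretionary powers, which are real.

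The conclusion assumes that investigators follow 9.1.1 as written and that the unseen charter and DMC analysis plan do not already supply the table. If they do, only a cross-reference is missing. Nor should a reader infer that any dosing decision in this trial was affected: SAP 1.1 records termination with 3 subjects randomised in a partly enrolled first cohort, so no escalation took place and the point concerns the design.

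**What to change.** - **Protocol 10.4:** add the predefined complications of prematurity, by dose cohort and placebo and whatever their attribution, to the endpoints for each escalation review. Label the table descriptive.
- **Protocol 10.7:** state that the DMC weighs these complications, together with all TEAEs and deaths, when it recommends on escalation. The decision stays a matter of DMC judgement.

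No change to the DLT attribution rule in 6.3 is needed for this.

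The cost is a few lines of text and one more table. The data are already collected at every visit, and an independent external consultant already prepares the DMC analyses, so the blinding arrangements do not change. The downside is the risk of over-reading chance imbalances at 4 v 2, which the descriptive label is meant to limit.
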